# 7.7 Protocol Deviations/ Violations

#### 7.7.1 Protocol Deviation

A protocol deviation can be defined as any accidental or unintentional change to, or non-compliance with the research protocol that **does not** increase risk or decrease benefit or, **does not** have a significant effect on the participant's rights, safety or welfare; and/or on the integrity of the data. Deviations may result from the action of the participant, researcher, or research staff.

A deviation may be due to the participant's non-adherence, or an unintentional change to or non-compliance with the research protocol on the part of a researcher.

Examples of a deviation include, but are not restricted to:

- A rescheduled trial visit.
- Participant refusal to complete scheduled research activities.

Deviations will be documented on a trial specific CRF and reported to the TMG and TSC as agreed in the Trial Monitoring Plan (TMP).

#### 7.7.2 Protocol Violation

A protocol violation can be defined as any accidental or unintentional change to, or non-compliance with the protocol that **does** increase risk or decrease benefit, or has a significant effect on the participant's rights, safety, or welfare, or on the integrity of the data.

Examples of a violation include, but are not restricted to:

- Failure to obtain valid informed consent.
- Breaches of eligibility criteria.

#### 8. INTERVENTION AND COMPARATOR

#### 8.1. Intervention: Blended Behavioural Activation

#### 8.1.1 Content

"Be Active" (13) workbooks (8 sessions) have been developed to include blended delivery plus TAU+psychoeducation versus TAU+psychoeducation. The BA program is designed to be structured, yet flexible in delivery. Each BA workbook consists of an overview of the session, agenda, symptom and risk check, homework review, session content, session summary (feedback and goals review) and carer information. The first 4 sessions focus on introducing BA, goals, values, and activity scheduling (See Table 4)

The BAY BA training programme has 3 components: a clinician's manual which includes guidance on providing remote delivery, cultural adaptation, and links to demonstration videos; training to use workbooks including understanding of fidelity ratings, cultural issues, and remote delivery (initial 2 days training plus 2 further days led by local therapy leads which will include practice case discussion); and required reading of existing material on behavioural activation and depression (RCPsych/minded.org).

A website for blended delivery will be developed in order to enhance our current basic website in order to improve the experience of remote therapy, and will include animations. Young people fed back that our original website was easy to use, but would benefit from more functionality and improved design. Therefore, in the first phase of the study, we will co-design an enhanced platform with YP, focussing on making the site more engaging, usable, safe and accessible. The platform will comply with NHS Digital-recommendations, and will not be a Medical Device. We will use Agile methodology and track analytics to understand how the platform supports intended outcomes (Yardley et al, 2016). Development will include 4 co-design workshops with YP (n=4) and members of the research and software teams. In month 7, we will beta-test with 5 healthy volunteer YP, 5 professionals, & assess user acceptance in month 8.

**Table 4:** Eight BA modules in BAY

Module	Topics covered
Module 1: Goal setting, Psychoeducation and Recording	
 
Engagement, personalisation, getting to know the young people and establishing a therapeutic rapport
 
Setting out rationale and contents of the programme
 
Finding person-centred ways to plan and record activities
 

Module 2: Introduction to Valued Living	
 
Understanding the value of the effort that the young person makes outside of therapy sessions
 
Introduction of 'ACEs': Measures of Achievement, Closeness and Enjoyment
 

Module 3: Values	Fun (leisure), Work (school), Relationships (family
Clarification	and/or friends), Self-care (sleep, eating, exercise)
	How to personalise values and link them to key
	tasks
	Clarifying that values are "owned" by the young
	person
	Encouraging and expecting the recording of
	activities and address any barriers to doing this if
	identified
Module 4: Activity Planning	Young person should be in a routine of recording
and Addressing Barriers	activities linked to values and ratings of enjoyment
	and achievement
	Break down more challenging tasks into small steps
	Explore options for support to engage in planned
	activities
	Developing a personalised activity log
Module 5: Rewards and	Reviewing theory of behavioural activation and
Getting Support	getting support via rewards
	Conversation about types of rewards (social,
	material and self-rewards)
	Planning rewards for successful activity planning
	and achievement
	Being positive and looking for evidence of progress      SMART and looking for evidence of progress
Mad la C A aida aa	(using SMART goals)
Module 6: Avoidance	Triggers, Responses and Avoidance Patterns     Triggers, Responses and Avoidance Patterns
Patterns – TRAP(s)	(TRAPs)
	Seeking and exploring young person's unhelpful but typical patterns and habits of avoidance
Module 7: Problem Solving	Triggers, Responses and Alternative Coping (TRAC)
- TRAC	
 
Exploring personalised and real-life examples of
 

- TIME	problems to teach problem-solving skills and
	develop alternative coping behaviours
	Collaborative work
	
 
Encouragement for young person to identify their
 

	own solutions
Module 8: Staying Well and	Developing a relapse prevention plan between
Review	therapist and young person
	Revisit rationale for BA, document advice about
	potential low mood triggers and warning signs of
	relapse, and review and summarise what has been
	helpful for the young person during the
	programme.
	Signposting to additional sources of support and
	accessible resources

# 8.2 COMPARATOR: Psychoeducation plus Treatment as Usual

Following randomisation, all young people will receive a website link to a psychoeducation leaflet from the Royal College of Psychiatrists. The leaflet provides information about depression and signposting to where young people can find extra support. Carers (if involved) will also receive carer information regarding depression in young people, as well as signposting for carers.

Usual practice in CAMHS can vary widely (experience of the trial team and in national reports eg CQC 2018). Treatment as usual may be no intervention whilst on an internal CAMHS pathway waiting list; signposting to alternative sources of support; risk and case management; referral to a psychiatrist for medication review; or referral for psychological therapy, however, these generally have long waiting lists. Currently waiting lists for therapy in CAMHS services vary and can be months.

We will record and monitor what treatment as usual means for each young person recruited into the study. We will devise a pro-forma for RAs to complete using clinical records. This will capture all interventions that were delivered in CAMHS, including BA, and recording of risk issues such as attendance at A&E.

When reviewing clinical records we will particularly look for any aspects of treatment as usual that are similar to BA e.g. rating and structuring activities. Even in sites where BA-type interventions may be included in treatment as usual (such as brief psychosocial support), from experience within the associated teams, it is expected that these interventions are sufficiently different to our BA. For example, they are not standardised or do not include key components such as activity scoring.

# 8.3 Delivery

The BAY therapist will be the first point of contact within the CAMHS team for the Trial Managers. Therefore, immediately after randomisation, the Trial Managers from YTU will contact the BAY therapists (and their clinical supervisor) to inform them of the young person's allocation. The Trial Managers will also inform the young person and their carer (if applicable) of their allocation. For the intervention arm, the BAY therapist will then contact the YP to arrange the first session and begin delivering behavioural activation.

BA will be delivered by trained members of staff based within CAMHS. Given that part of our study's rationale is that BA can be disseminated by professionals with less therapy training and who are less expensive to employ, we will exclude professionals on or above NHS pay grade 6 who are usually experienced qualified clinicians. Professionals in CAMHS whose role is to work with young people with mental health and emotional difficulties and who are below grade 6, include: assistant psychologists (APs), education mental health practitioners (EMHPs), children's wellbeing practitioners (CWPs), newly qualified nurses. These will be supported by a grade 7 supervisor within CAMHS, including clinical psychologists and experienced CBT therapists. A lead psychologist and co-applicant on the trial will oversee all supervision for BAY therapists and their supervisors.

There will be at least two trained BAY therapists within each NHS Trust. If one therapist cannot continue delivering BA with a young person, the other trained therapist will be allocated to that young person. If a therapist ceases to be involved in BA delivery, the PI

and psychology lead at the site will identify whether there are any other suitable Band 4 or 5 clinical professionals within the CAMHS service. If so, they will be trained to deliver BA. If not, a band 4 or 5 clinical professional will be recruited internally or externally and trained to deliver BA. This will ensure there are two BA therapists at site.

To enable the collection of data on procedural fidelity, we will ask therapists to complete a procedural fidelity checklist at the end of each session. With the participants consent all therapy sessions will be audio recorded to enable assessment of BA fidelity on 10% of sessions at the end of the trial.

# 8.4 Identifying and mitigating contamination

Pathways to, and sources of, contamination

Contamination would occur if young people randomised to treatment as usual receive elements of BA. This may happen for the following reasons:

- At service level: Treatment as usual services offer BA as a standalone intervention or elements of BA as part of another intervention, such as cognitive behaviour therapy.
- At professional/therapist level: Professionals supporting young people in treatment as usual inadvertently or deliberately deliver BA. This can happen if professionals: have previously been trained in BA; received BA training as part of BAY and support participants in both BA and treatment as usual arms; access BA resources on their own accord online or publicly available treatment manuals (e.g. prompted by reading about BA in the BAY protocol).
- At participant level: Participants randomised to treatment as usual access BA materials.

#### Preventing contamination

- Where possible, sites will identify separate professionals to support BA and treatment as usual for participants in the trial. If the same professional delivers both BA and treatment as usual, the BA trainer and supervisor will ask the professional to avoid using any resources, principles or techniques of BA as part of treatment as usual.
- Access to the BAY manual alone, previous training, or self-directed learning are not sufficient to deliver BA at a standard that will be considered 'contamination in BAY'; this requires training by the research team plus consistent supervision to be able to deliver BA with fidelity.
- A Contamination Information Sheet (CIS) outlining what 'contamination' of treatment as usual is, why it is important to prevent it in BAY, how to prevent it, and what to do if it happens. The CIS will be included in the local information pack sent to the participating sites and in the BA training pack for professionals.
- The importance of avoiding contamination will be covered in detail at the two-day training event for BAY therapists. BAY therapists and their supervisors who attend the training will be asked to disseminate this information to their CAMHS service.

# Monitoring Contamination

- Training: Therapists and supervisors will be informed at the BA initial training event about the importance of avoiding contamination in the TAU arm post randomisation. BAY leads will then disseminate information to clinics and managers and regularly remind them of this.
- At sites: BA therapists will avoid delivering regular sessions to young people allocated to treatment as usual alone post randomisation, in conjunction with managers/site leads.
- Aspects of care questionnaire: All YP to complete an 'aspects of care questionnaire' which asks about BA elements of their treatment from any source at follow up (including external to CAMHS).

# Addressing Contamination

- We will assess contamination as above as part of the 8 month internal pilot by reviewing the Aspects of Care questionnaire.
- If contamination is present (or suspected) in a site, the research team will contact the site and discuss ways to mitigate this e.g. identifying alternative professionals to deliver treatment.

#### 9. STATISTICAL AND DATA ANALYSIS

# 9.1 Sample Size

For 90% power to detect an effect size of 0.3125 we will require 8 groups of 28 in the intervention arm and 224 individuals in the control arm, giving a total of 448 participants. This effect size corresponds to a minimally important difference of 5 points on the MFQ-C(Wood et al., 1995) with a standard deviation of 15. This calculation was performed in Stata using the 'clsampsi' command and includes a baseline-follow up correlation of 0.41 and an ICC of 0.01 in the intervention arm. Parameter estimates were informed by our feasibility study and previous IMPACT trial (Goodyer et al., 2017; Goodyer et al., 2007,). 7% attrition was observed at 6 months in the HTA ADAPT trial and 16% in IMPACT, however this was at 18 months. Conservatively inflating the current sample size by 15%, we will recruit a total sample size of 528.

On 28th April 2025the funder approved a request from the study team for a costed extension, under the condition that the sample size be recalculated to provide 80% power. Assuming based on the trial data collected so far an updated baseline-follow-up correlation of 0.45, 13 groups of 12 participants in the intervention arm, a 70% retention rate, an effect size of 0.30 and keeping all other parameters the same, 446 participants (223 per group) are required for 80% power to detect a minimum clinically important difference of five points on the MFQ-C.

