# 9.2 Statistical Analysis

Analyses will be conducted in Stata version 17 (or later) following intention-to-treat principles and will follow a detailed pre-specified statistical analysis plan. Statistical

significance will be assessed at the 5% level unless otherwise stated, and 95% confidence intervals will be provided as appropriate. Analyses and results will be reported according to CONSORT guidelines. The flow of individuals through the trial will be reported in a CONSORT diagram, including the number screened (and reasons for ineligibility) and approached for consent (and reasons for non-consent), the number randomised, adherence to allocated treatment, follow-up data completeness and the number of participants included in the primary analysis. Descriptive summaries of continuous data by trial arm will be given in terms of the mean and standard deviation (or median and inter quartile range as appropriate). Descriptive summaries of categorical data will be given in terms of frequencies and proportions. No formal statistical testing will be conducted at baseline. Information on intervention delivery including number and duration of sessions will be summarised descriptively.

The primary outcome (total MFQ-C score) will be summarised descriptively at each time point and analysed using a mixed-effects linear regression model, including all available time points. The model will include trial arm, time, arm-by-time interaction, baseline MFQ score and other important baseline variables as fixed effects. Random effects will be included to account for the repeated measures within patients and for possible clustering by therapist (nested within treatment arm). The primary analysis will compare the groups at 6-months post-randomisation. Secondary analyses will compare the groups at 12-weeks and 12-months post-randomisation. Different covariance patterns for the repeated measurements will be explored and the most appropriate pattern will be used for the final model. Data will be assumed missing at random. Secondary outcomes will be analysed using similar models as described above (with binary outcomes being analysed using a mixed-effects logistic regression model), adjusting for the same fixed and random effects.

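### Section 9.1 equates five MFQ-C points with effect sizes of 0.3125 and 0.30, neither of which follows from the only SD stated (15), so the 80% power for five points does not follow from it

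*Protocol*

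**What the plan says.** Section 9.1 of the protocol holds two calculations.

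- **First paragraph.** It begins "For 90% power to detect an effect size of 0.3125", using "8 groups of 28 in the intervention arm and 224 individuals in the control arm, giving a total of 448 participants". It ties the effect to the raw scale: "This effect size corresponds to a minimally important difference of 5 points on the MFQ-C(Wood et al., 1995) with a standard deviation of 15". The calculation "includes a baseline-follow up correlation of 0.41 and an ICC of 0.01 in the intervention arm".
- **Second paragraph**, added after the funder's decision of April 2025. It is introduced as resting on the trial data so far. It lists a correlation of 0.45, 13 intervention-arm groups of 12 and 70% retention, and ends with "an effect size of 0.30 and keeping all other parameters the same, 446 participants (223 per group) are required for 80% power". The target is again five points on the MFQ-C.

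No outcome SD other than 15 appears in the protocol. The move from 0.3125 to 0.30 is not explained.

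**The concern.** A raw difference, an SD and a standardised effect are bound by one identity: effect = difference / SD. Section 9.1 gives all three in its first paragraph, and they do not satisfy it. The second paragraph changes the effect, keeps the difference and gives no new SD.

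This is the protocol's current power statement, and recalculating to 80% power was a condition of the funded extension. As written, a reader cannot tell whether 446 participants give 80% power for five points, or 80% for 4.5 points and noticeably more for five.

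**Working it through.** **Conversion**

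- 5 / 15 = 0.333, which is neither 0.3125 nor 0.30. Rounding does not bridge the gap.
- 0.3125 for five points needs SD = 5 / 0.3125 = 16. At SD 15 it is 0.3125 × 15 = 4.69 points.
- 0.30 for five points needs SD = 5 / 0.30 = 16.7. At SD 15 it is 0.30 × 15 = 4.5 points.

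**Power model**

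Inputs are from section 9.1, with the 5% level from section 9.2. A two-sided test is assumed; 9.1 does not say so, but 9.2 plans 95% confidence intervals. Clustering applies in the intervention arm only:

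SE² = (1 − r²) × [(1 + (m − 1) × ICC) / (k × m) + 1 / n_control], in SD units.

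Power comes from the noncentral t distribution with Satterthwaite degrees of freedom.

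**Reproducing the first calculation** (k = 8, m = 28, n_control = 224, r = 0.41, ICC = 0.01)

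- 1 − 0.41² = 0.8319; design effect 1 + 27 × 0.01 = 1.27.
- SE² = 0.8319 × (1.27 + 1) / 224, so SE = 0.0918; df about 22.
- At 0.3125, power is 90.2%, which matches the stated 90%.
- At 0.333 (five points, SD 15), power is 93.4%.

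**Reproducing the revised calculation** (k = 13, m = 12, n_control = 156, r = 0.45, ICC = 0.01)

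- 13 × 12 = 156 analysed per arm; 156 / 0.70 = 222.9, so 223 per arm and 446 in total, as stated.
- 1 − 0.45² = 0.7975; design effect 1 + 11 × 0.01 = 1.11.
- SE² = 0.7975 × (1.11 + 1) / 156, so SE = 0.1039; df about 41.
- At 0.30, power is 80.5%, which matches the stated 80%. Twelve clusters would give 77.1%, so 13 is the smallest whole number that reaches 80%.

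Both sample sizes therefore follow from the printed effect sizes.

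**Power of the revised design for a true five-point difference**

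| SD | 5 / SD | Power (t) | Power (normal) |
|---|---|---|---|
| 15 (stated) | 0.333 | 88.0% | 89.4% |
| 16 (implied by 0.3125) | 0.3125 | 83.6% | 85.3% |
| 16.7 (implied by 0.30) | 0.30 | 80.5% | 82.3% |

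**Size in participants**

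At SD 15, 80% power for five points needs 11 whole clusters of 12. That is 132 analysed per arm, and 132 / 0.70 rounds up to 189, so 378 recruited. Allowing fractional clusters gives about 361. Against 446 the gap is 446 − 378 = 68 to 446 − 361 = 85.

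**The case against.** The best defence is that 0.30 is a declared update. It stands in a list introduced as based on trial data, and the other parameters held fixed are naturally those outside the list, such as the ICC and the 5% level. If the target is still five points, the simplest explanation is that the observed SD had risen to about 16.7. The 446 and the 80% would then both be right. This is plausible, so it goes too far to say that the SD was altered covertly. But the protocol gives no such SD, and the explanation leaves the first paragraph's equation wrong.

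A reader might be tempted to infer more:

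- **That the trial is underpowered.** The documents do not support this. Power for five points is at least 80% at every SD stated or implied, and if SD 15 holds the slip is conservative. Power falls below 80% only with a larger SD (79.0% at SD 17), and nothing in the protocol points to one.
- **That 446 is the wrong number.** It follows from the printed effect of 0.30. The gap of 68 to 85 participants arises only if SD 15 is the true planning value.
- **That a null result could not be read.** It would be read from the observed confidence interval against five points, and the planning SD does not change that interval. What is unclear is the design power quoted beside it.

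**Conclusion.** The inconsistency is certain and can be checked from section 9.1 alone. Two standardised effects are printed for the same five points, and neither equals five divided by the stated SD. The fault lies in the conversion; the sample-size arithmetic is sound. The stated 80% power for five points does not follow from SD 15, where it is about 88%. It holds if the SD is about 16.7.

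The power figures assume a two-sided 5% test, 156 analysed per arm, r = 0.45 and ICC = 0.01 in the intervention arm only. The documents cannot settle which SD lies behind 0.30; only the trial team can. Recruitment and analysis are unaffected, so this should be fixed but is not critical.

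**What to change.** Keep N = 446 and correct section 9.1 at the next amendment.

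1. **First paragraph:** change the SD to 16, or keep SD 15 and give the effect as 0.333, with power of about 93% for the 448 analysed.
2. **Second paragraph:** state the SD behind 0.30 and where it came from. Replace the general clause about unchanged parameters with the ones meant (ICC 0.01, 5% level). Do not simply delete it, because it is the only text that carries the ICC into the revised calculation.
3. **If the SD is still 15:** state instead that 446 gives 80% power for 4.5 points and about 88% for five.

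The cost is a few words in one section, with no change to recruitment, design or analysis.

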# 9.2 Statistical Analysis

Analyses will be conducted in Stata version 17 (or later) following intention-to-treat principles and will follow a detailed pre-specified statistical analysis plan. Statistical

significance will be assessed at the 5% level unless otherwise stated, and 95% confidence intervals will be provided as appropriate. Analyses and results will be reported according to CONSORT guidelines. The flow of individuals through the trial will be reported in a CONSORT diagram, including the number screened (and reasons for ineligibility) and approached for consent (and reasons for non-consent), the number randomised, adherence to allocated treatment, follow-up data completeness and the number of participants included in the primary analysis. Descriptive summaries of continuous data by trial arm will be given in terms of the mean and standard deviation (or median and inter quartile range as appropriate). Descriptive summaries of categorical data will be given in terms of frequencies and proportions. No formal statistical testing will be conducted at baseline. Information on intervention delivery including number and duration of sessions will be summarised descriptively.

The primary outcome (total MFQ-C score) will be summarised descriptively at each time point and analysed using a mixed-effects linear regression model, including all available time points. The model will include trial arm, time, arm-by-time interaction, baseline MFQ score and other important baseline variables as fixed effects. Random effects will be included to account for the repeated measures within patients and for possible clustering by therapist (nested within treatment arm). The primary analysis will compare the groups at 6-months post-randomisation. Secondary analyses will compare the groups at 12-weeks and 12-months post-randomisation. Different covariance patterns for the repeated measurements will be explored and the most appropriate pattern will be used for the final model. Data will be assumed missing at random. Secondary outcomes will be analysed using similar models as described above (with binary outcomes being analysed using a mixed-effects logistic regression model), adjusting for the same fixed and random effects.

Sensitivity analyses assessing the robustness of results to deviations from the missing at random assumption will be carried out. We will also explore potential associations between therapist characteristics and outcomes. If any such associations are found, a sensitivity analysis will be carried out repeating the primary analysis with the addition of any confounding therapist characteristics as fixed effects.

The efficacy of the intervention in participants who complied with the intervention will be assessed using Complier-Average-Causal-Effect (CACE) analysis.

Any planned subgroup analyses will be pre-specified in the statistical analysis plan.

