#### 3.3. Quantitative Outcomes

Measures will be administered to participants by a trained researcher at baseline (n=446), 12 weeks (n=446), 6 months (primary outcome, n=446), and 12 months post-randomisation (naturalistic follow up, n= approx. 300/participants recruited  $\geq 12$  months before trial end date). All measures and their time-points of completion are presented in Table 1.

 Table 1: Summary of assessments

			TIMELINE				
Assessment	Source	Method of Completion	Screening	Baseline	12 Weeks	6 Months	12 Months *
			PARTICIPANT- YOU	NG PERSON			
Screening	Screening Log	Research Assistant (RA) /Site staff	X				
Mood and Feelings Questionnaire (MFQ-C)	Questionnaire	Self-completion	X	Х	Х	Х	X
Contact Details	CRF	Research Assistant/Participant		X	YTU to be notified of changes to contact details		itact details
Demographics	CRF	Self-completion/RA assistance if requested		X			
Eligibility (including Inclusion and Exclusion Criteria)	CRF	PI/Research Assistant/PIs Delegate at site		Х			
Consent	Paper/Online Consent Form/REDCap	Self-completion / Research Assistant		Х			
Strengths & Difficulties Questionnaire (SDQ)	Questionnaire	Self-completion/RA assistance if requested		X	Х	Х	X
Development and Well- Being Assessment (DAWBA)	Online	RA led alongside participant if requested		X			
Revised Children's Anxiety and Depression Scale (RCADS) Brief Version	Questionnaire	Self-completion/RA assistance if requested		Х	Х	Х	Х

Behavioural Activation for Depression (BADS)	Questionnaire	Self-completion/RA assistance if requested		X	Х	X	X				
Self- harm & suicidality questions	CRF	Self-completion/RA assistance if requested		Х	Х	Х	Х				
Goal based outcomes	CRF	Self-completion/RA assistance if requested		X	X	Х	X				
Child Health Utility -9 Dimensions (CHU-9)	Questionnaire	Self-completion/ RA assistance if requested		Х	Х	Х	X				
EQ-5D-Y	Questionnaire	Self-completion/RA assistance if requested		X		Х					
Healthcare Service Use schedule	CRF	Self-completion (with assistance from carer)		X	X	Х	X				
Aspects of Care Contamination Checklist	CRF	Self-completion/RA assistance if requested			X	Х	X				
Working Alliance Inventory (WAI-S)	Questionnaire	Self-completion	(Collected halfway through intervention delivery)								
End of BA treatment Questionnaire	Questionnaire	Self-completion	(Collected after final session of BA therapy)								
Optional Qualitative Interview	Semi-structured interview	Interview				X					
			PARENT/CA	RER							

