#### 7.5.3 Treatment discontinuation

In line with usual clinical care, cessation or alteration of trial treatment at any time will be at the discretion of treating clinicians or the participant themselves who may choose to withdraw from the study intervention at any time.

A clinician may decide that a participant should be withdrawn from the research trial if there is reason to believe that they have, after screening and consent, become unsuitable for the study such that the study could become harmful or interfere with other necessary treatments. Reasons for withdrawal could include:

- Very high prolonged risk such as active suicidal behaviours/plans and imminent intent;
- Indication that the intervention is leading to a clear worsening of mental health;
- Further or emergent physical or mental health problems that may exclude the possibility of engagement in the intervention;
- Loss of the capacity to consent to participate in the trial;
- Significant issues with addiction to alcohol or drugs;

If any of these situations for withdrawal occur, the clinician identifying the issue will follow their usual practice within their Trust and notify the PI at the recruiting site.

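### The listed primary model gives baseline MFQ one slope for all three follow-ups; adding baseline-by-time is a cheap safeguard for the 6-month contrast

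*Protocol*

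**What the plan says.** Protocol section 9.2 says that total MFQ-C will be "analysed using a mixed-effects linear regression model, including all available time points". The follow-ups are 12 weeks, 6 months and, for those recruited early enough, 12 months (section 3.3: "naturalistic follow up, n= approx. 300/participants recruited"). The fixed effects are given in one sentence: "The model will include trial arm, time, arm-by-time interaction, baseline MFQ score and other important baseline variables as fixed effects". Arm-by-time is the only interaction named. The primary contrast is fixed: "The primary analysis will compare the groups at 6-months post-randomisation". On missing data: "Data will be assumed missing at random", and "Sensitivity analyses assessing the robustness of results to deviations from the missing at random assumption will be carried out". Secondary outcomes use similar models with the same adjustment.

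Section 9.1 plans for "a 70% retention rate" and gives a single baseline-to-follow-up correlation of 0.45, with no values by visit. Section 9.2 also refers to a detailed SAP, which was not available for this review.

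**The concern.** A baseline score often predicts an early visit better than a late one. A model with a single slope then fits a compromise between the visits, and that compromise need not be right at 6 months. While the participants observed at 6 months have the same baseline mix in both arms, this hardly matters, because the adjustment multiplies a difference close to zero. If loss leaves the arms with different baseline means, the wrong slope over- or under-corrects for that difference, and the error goes into the treatment effect.

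This can happen with data missing at random given baseline. The planned sensitivity analyses examine departures from that assumption, so they are not aimed at this error. What is at stake is the primary result, and the same form is carried to the secondary outcomes.

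**Working it through.** **Inputs from the protocol.** 446 randomised (223 per arm); 70% retention; correlation 0.45; effect size 0.30 for 5 points, which implies SD 5/0.30 = 16.7; ICC 0.01 with 13 groups of 12 in the intervention arm; about 300 of 446 due a 12-month visit. (Section 9.1 also states SD 15, and the first calculation's 0.3125 implies SD 16. The runs below use 16 or 16.7.)

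**Step 1: reproduce the plan's figure.** Analysed per arm: 13 × 12 = 156. Randomised: 312/0.70 = 445.7, so 446. Variance factor: 1 − 0.45² = 0.7975. Design effect in the intervention arm: 1 + 11 × 0.01 = 1.11. SE in SD units: √(0.7975 × (1.11 + 1)/156) = 0.104. Normal-approximation power: Φ(0.30/0.104 − 1.96) = 82.3%. A t-test with Satterthwaite degrees of freedom gives 80.5%. The stated 446 for 80% power is reproduced.

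**Step 2: what the common slope does.** Let b_c be the fitted common slope, b_6 the true 6-month slope (points per baseline SD), and Δ the arm difference (BA minus control) in mean baseline, in SDs, among those observed at 6 months. To first order:

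shift in the 6-month effect ≈ −(b_c − b_6) × Δ

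It vanishes if the slope is constant (b_c = b_6) or if Δ = 0. With SD 16.7, b_6 = 0.45 × 16.7 = 7.5. For correlations 0.55/0.45/0.35 and loss depending on baseline in opposite directions in the two arms, the fitted values were b_c = 8.23 and Δ = 0.46, giving −(8.23 − 7.5) × 0.46, about −0.3. The full model gave −0.44, because the misfit at 12 weeks also reaches 6 months through the within-person correlation.

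**Step 3: large-sample simulation.** Unstructured covariance, maximum likelihood, no therapist effect, true effect −5, SD 16.7, 30% lost by 6 months and half of that by 12 weeks. Baseline dependence is 0.8 on the log-odds scale per SD (odds ratio e^0.8 = 2.2). The 12-week and 12-month correlations are assumptions. Entries are the common-slope estimate minus the baseline-by-time estimate, in points; negative favours BA.

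| Loss pattern | 0.45/0.45/0.45 | 0.55/0.45/0.35 | 0.65/0.45/0.25 | 0.25/0.45/0.25 |
|---|---|---|---|---|
| Completely at random, or same baseline dependence in both arms | 0.00 | at most 0.02 | at most 0.02 | at most 0.02 |
| Same dependence, 20% vs 40% lost | 0.00 | +0.16 | +0.36 | −0.37 |
| Dependence in control only | 0.00 | −0.22 | −0.55 | +0.55 |
| Opposite dependence | 0.00 | −0.44 | −1.11 | +1.10 |

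With weaker dependence (odds ratio 1.5 per SD), SD 16, and correlations 0.55/0.45/0.35 or 0.65/0.45/0.35, the size of the shift is about 0.1 to 0.3 when one arm only is affected and about 0.2 to 0.6 when the arms go in opposite directions. At odds ratio 2 in opposite directions it is about 0.4 to 1.

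**Step 4: coverage and cost at trial size** (446 participants, 1,500 replicates, Step 3 settings, one-arm and opposite dependence). Coverage of the 95% interval with the common slope is 94.0% to 94.5% for 0.55/0.45/0.35 and 90.2% to 92.6% for 0.65/0.45/0.25. In the worst of these the interaction restores it from 90.2% to 94.9%. Across all scenarios the 6-month model SE changes by between −1.0% (1.655 to 1.639) and +1.5% (1.660 to 1.685). With equal slopes, power changes by less than one percentage point.

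**The case against.** The strongest reply is that section 9.2 is an outline. It leaves the other baseline variables unnamed and the covariance pattern open, and it refers to an SAP that may well contain the interaction. That stands to this extent: the protocol does not exclude the term, so this is a request to state or confirm it. It does not remove the point, because the sentence lists the fixed effects and names arm-by-time as the only interaction.

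Several stronger readings are tempting and are not supported:

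- A reader might infer that 30% loss by itself biases the result. It does not. With equal slopes the shift is 0.00, and with loss that does not differ by arm it is at most 0.02.
- A reader might take the withdrawal reason in section 7.5.3, "Indication that the intervention is leading to a clear worsening of mental health", as evidence of the required loss pattern. It describes worsening after randomisation, not baseline severity. Section 7.5.2 also separates stopping BA from stopping questionnaires. If such worsening is unobserved and drives loss, the data are not missing at random and the interaction does not help.
- A reader might expect a bias in a known direction. The sign depends on correlations that the protocol does not give, and Step 3 produces both signs.
- A reader might headline the 1-point case. It needs baseline to predict loss strongly and in opposite directions in the two arms, which nothing in the protocol suggests.

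The simulations also omit the therapist effect and the other covariates.

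**Conclusion.** The point holds as a low-severity, cheap improvement. As listed, the model imposes one baseline slope on three visits. If the slope changes over time and baseline-related loss differs by arm, the 6-month contrast is biased under the plan's own missing-data assumption. If either condition fails, the shift is nil. The protocol is silent on both.

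Under moderate assumptions the shift is 0.1 to 0.3 points, which is 2% to 6% of the 5-point difference and under one-fifth of a standard error of about 1.6 (0.3/1.6 = 0.19). With opposite dependence at odds ratio 1.5 it is up to about 0.6 points (12%), and near 1 point only in extreme cases. These figures rest on assumed 12-week and 12-month correlations and assumed loss patterns. The case for the change is that it protects the primary contrast at almost no cost, not that a bias has been shown.

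**What to change.** In section 9.2, give the fixed effects as trial arm, time, arm-by-time, baseline MFQ, baseline-MFQ-by-time and the other baseline variables. For secondary outcomes measured at more than one follow-up, use the outcome's own baseline and its interaction with time. If the SAP already specifies this, confirming so before any unblinded analysis is enough.

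The cost is one phrase and two extra parameters, with about 312 participants expected to be analysed at 6 months, no new data, and at most about 1% to 1.5% on the standard error. The term corrects only this misspecification. The planned sensitivity analyses for data not missing at random are still needed.
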